9.2. Vital Sign Measurements

Summary tables will be presented for vital sign data, including systolic blood pressure (mmHg), diastolic blood pressure (mmHg), temperature (C), heart rate (bpm), height(cm) and body weight(kg) by treatment group and overall for participants in the Safety set. Observed results at each visit and changes from baseline to each scheduled post-baseline visit will be presented. All vital sign data by participant will be presented in a listing.

9.3. Ocular Safety Data

9.3.1. Best Corrected Visual Acuity (BCVA)

Best-Corrected Visual Acuity (BCVA) will be measured in each eye prior to cycloplegia with the participant wearing current correction using the Early Treatment of Diabetic Retinopathy Study (ETDRS) testing protocol. If the vision is more than 1 line (≥ 5 letters) worse than baseline, the testing will be redone using trial frames or phoropter with the most recent subjective refraction.

Changes in BCVA will be summarized for the Safety Set and subgroups (Age, Sex, Race and Iris Color) based on the following categories:

- ≥ 15 letters gained
- ≥ 10 letters but < 15 letters gained
- ≥ 5 but < 10 letters gained
- No change (< 5 letters change)
- ≥ 5 but < 10 letters lost
- ≥ 10 but < 15 letters lost
- ≥ 15 letters lost

Shift in BCVA from baseline will be measured for most recent assessment (i.e., the last available assessment prior to or on the analysis cut-off of Month 24, Month 36, Month 48) and worst-post baseline assessment at Month 24, Month 36 and Month 48 for each treatment received. The average of BCVA from the right and left eyes will be used for analysis.

9.3.2. Binocular Near Visual Acuity

Binocular Near Visual Acuity will be measured using the ATS4 Near Acuity Test with participants wearing current refractive correction prior to administration of cycloplegia on a bi-annual basis and results in Snellen equivalents will be recorded on the eCRF. Changes in near visual acuity at most recent post-baseline visit (i.e., the last available assessment prior to or on the analysis cut-off of Month 24, Month 36, Month 48) and for the worst post baseline assessment will be summarized based on the following categories:

- ≥ 3 lines gained
- ≥ 2 but < 3 lines gained
- ≥ 1 but < 2 lines gained
- No change (< 1 line change)
- ≥ 1 but < 2 lines lost
- ≥ 2 but < 3 lines lost
- ≥ 3 lines lost

Line changes will be derived from the LogMAR equivalent scores using the following formula such that a positive value indicates a worsening/loss and a negative value indicates an improvement/gain:

LogMAR = $-\log(20/\text{denominator of Snellen fraction})$

Line change = $10 \times [-\log(20/\text{dfollow-up}) - (-\log(20/\text{dbaseline}))]$,

where follow-up is the denominator of the Snellen fraction at a post-baseline visit
dbaseline is the denominator of the Snellen fraction at Baseline
log is logarithm base 10.

For example, the line change for a Snellen visual acuity at Baseline of 20/20 followed by a Snellen VA of 20/15 would be $10 \times [-\log(20/15) - (-\log(20/20))]$ = -1.25 and represent an improvement/gain of 1.25 lines in visual acuity.

The number and percentage of participants with categorized line change will be summarized by treatment group. The eye with the most lines lost/least lines gained will be summarized.

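### Unrounded near-acuity line changes are cut at exactly 1, 2 and 3 lines, so on standard Snellen steps many one-line changes would be tabulated as no change

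*SAP*

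**What the plan says.** Protocol 8.2 and SAP 9.3.2 have near acuity tested binocularly with the ATS4 Near Acuity Test. SAP 9.3.2 adds that "results in Snellen equivalents will be recorded on the eCRF". Protocol 8.2 refers to the Manual of Procedures for assessment details, and neither document lists the chart's acuity steps.

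SAP 9.3.2 then states: "Line changes will be derived from the LogMAR equivalent scores using the following formula". LogMAR is minus the log of 20 over the Snellen denominator, and line change is ten times follow-up logMAR minus baseline logMAR. The section specifies that "log is logarithm base 10" and sets the sign "such that a positive value indicates a worsening/loss and a negative value indicates an improvement/gain".

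The line change is sorted into seven classes. The middle one is "No change (< 1 line change"), and on each side there are classes for at least 1 but under 2 lines, at least 2 but under 3, and 3 or more. They are tabulated for the most recent and the worst post-baseline assessment. The section has no rounding step. Its worked example, 20/20 to 20/15, is kept as a gain of 1.25 lines. It closes with "The eye with the most lines lost/least lines gained will be summarized".

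**The concern.** The factor of ten makes one line equal to 0.1 logMAR, and the class boundaries sit exactly on whole lines. Snellen denominators, however, are rounded labels for steps of about that size. Putting them through an exact logarithm gives values slightly above or below the whole number, and the boundary then decides the class. Two children who each lose one chart line can land in different rows because they started on different lines.

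SAP 9.3.1 shows the contrast. It treats five letters as a line of distance acuity, and its lowest loss class starts at exactly five letters, so a one-line loss is counted. The near-acuity rule does not reliably do the same. At stake is a safety description: near vision is a natural place to look for a cycloplegic effect of atropine, and a one-line loss is the smallest change the table is built to show.

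**Working it through.** **Inputs from SAP 9.3.2.** Line change = 10 × [−log10(20/d_follow-up) − (−log10(20/d_baseline))], which simplifies to 10 × log10(d_follow-up / d_baseline). Cuts are at 1, 2 and 3, unrounded.

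**Assumed input.** The chart steps. Main series: 20/16, 20, 25, 32, 40, 50, 63, 80, 100, 125, 160, 200. Alternative: 20/15, 20, 25, 30, 40, 50, 60, 80, 100.

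**The plan's own example.** 20/20 to 20/15: 10 × log10(15/20) = −1.2494, shown as −1.25. It reproduces, so the formula is being read as intended.

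**One-step losses, main series.**

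| Step | Ratio | Line change | Class under the SAP |
|---|---|---|---|
| 16→20, 20→25, 32→40, 40→50, 80→100, 100→125, 160→200 | 1.25 | 0.969 | No change |
| 50→63 | 1.26 | 1.004 | One line lost |
| 63→80 | 1.270 | 1.037 | One line lost |
| 25→32, 125→160 | 1.28 | 1.072 | One line lost |

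So 7 of 11 one-step losses are tabulated as no change.

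**Two-step losses.** 16→25, 32→50 and 80→125 give 1.938, and 40→63 gives 1.973, all below 2. The other six lie between 2.007 and 2.041. So 4 of 10 drop a class.

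**Three-step losses.** 32→63 gives 2.942 and 63→125 gives 2.976, both below 3. The other seven give 3.010. So 2 of 9 drop a class.

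On this series the slippage is always towards less change: no one-step value reaches 2 and no two-step value reaches 3.

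**Gains.** Reversing a step only changes the sign. 20/25 to 20/20 is −0.969, also no change.

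**Alternative series.** 20→25, 40→50 and 80→100 give 0.969; 25→30 and 50→60 give 0.792; 15→20, 30→40 and 60→80 give 1.249. So 5 of 8 one-step losses fall below 1.

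**Is rounding specified elsewhere?** The rounding text in SAP Section 4 covers descriptive statistics, p-values and the display of averaged measures such as SE and axial length. It does not mention line change. Rounding to two decimals, as the worked example is displayed, would not help: 0.97 is still below 1.

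**With whole-line rounding.** All 11 one-step values (0.969 to 1.072) become 1, all ten two-step values (1.938 to 2.041) become 2, and all nine three-step values (2.942 to 3.010) become 3. The alternative one-step values (0.792 to 1.249) also become 1. The worked example becomes −1 and stays in the one-line-gain class.

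**The case against.** The strongest reply is that nothing is miscalculated. The SAP defines a line as 0.1 logMAR, its example reproduces, and by that definition 0.969 is less than one line. That stands as a description: the fault lies in placing hard cuts on values derived from rounded labels, not in the formula. Its practical consequence remains.

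Second, calling 20/20 to 20/25 one line rests on chart steps the documents do not give. This stands, and the finding is conditional on it. The SAP's example uses 20/15, which is not on the main series, but the alternative series includes 20/15 and shows the same problem.

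Third, many changes are classified correctly. From 20/20, two-line and three-line losses compute to 2.041 and 3.010. From 20/25, all three sizes of loss are right. Seven of nine three-line losses are right. This stands: the trouble is concentrated at the one-line cut.

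Fourth, the consequence is limited. The table is descriptive, and near acuity is not named separately among the safety endpoints in SAP 3.4 or Protocol Section 3. Accommodative amplitude is summarized continuously (SAP 9.3.5) and blurred vision by severity (SAP 9.3.9). Listings of the supporting raw data (SAP Section 4) would allow a recount. This stands too, and sets the weight of the point.

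A reader might infer that the rule hides an excess of near-vision loss on SYD-101. The documents do not support that. The rule is the same in all arms, it misses gains as well as losses, and no baseline acuity distribution or size of excess is given from which to work out a between-arm effect.

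**Conclusion.** The point holds as a classification defect in one descriptive safety summary. If the chart uses standard 0.1-logMAR steps labelled with Snellen denominators, the table under-counts small near-acuity changes in all arms, in both directions, and inconsistently by baseline line. The size is 7 of 11 possible one-line steps, 4 of 10 two-line and 2 of 9 three-line on the 20/16 to 20/200 series, or 5 of 8 one-line steps on the series with 20/30 and 20/60. These are counts of possible steps, not of children; how many participants are affected depends on baseline acuities that the documents do not report.

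No efficacy analysis is touched, and neither the direction nor the size of any effect on the comparison with Vehicle is established.

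The closing sentence about choosing an eye is a separate wording slip. A binocular test gives one value per visit, so there is no eye to choose. It adds no weight to the classification point.

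**What to change.** In SAP 9.3.2:

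- Round the computed line change to the nearest whole line before assigning the class, or count chart lines between baseline and follow-up directly.
- Relabel the classes as whole lines (0, 1, 2, 3 or more, gained or lost). Under rounding the effective cuts move to 0.5, 1.5 and 2.5, so the present labels would mislead.
- Restate the worked example: −1.25 rounds to a one-line gain, in the same class as now.
- State the ATS4 acuity steps recorded on the eCRF, so that a reader can confirm that one chart step maps to one line.
- Delete the sentence on the eye with the most lines lost and summarize the single binocular value.

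The cost is a few lines of SAP text and one programming step, with no new data. Any near-acuity table already produced would need to be rerun, and the reported frequencies of both loss and gain may rise.

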9.3.3. Dilated Ophthalmoscopy

An ophthalmoscopy examination will be performed with pupil dilation using an indirect ophthalmoscope as per the current standard of practice to evaluate the condition of the vitreous, macula, retina, optic nerve, choroid, and retinal periphery.

Ocular findings will be evaluated by the following criteria:

- Normal
- Abnormal (not clinically significant [NCS])
- Abnormal with clinical significance (clinically significant [CS])

The number and percentage of participants with at least 1 treatment-emergent clinically significant abnormality for any parameter and for each parameter will be summarized for each treatment group. At each level of summarization, a participant will be counted once even if the participant experiences more than one treatment-emergent clinically significant abnormality summarizing data for the worse eye. For analysis, the worse eye will be defined as the eye with the greater degree of abnormality where Abnormal CS > Abnormal NCS > Normal. An abnormality will be deemed treatment emergent if the onset date is on or after the date of first treatment. Data from all ophthalmoscopy assessments will be listed.

At Month 36 and Month 48 analyses, findings will be summarized for participants by current treatment at time of abnormality.

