| Dilated Ophthalmoscopy | X | X | | | X | | X | | X | | X | | X | | X | | X | | X | X |
| Randomization | | X | | | | | | | | | | | | | | | | X | | |
| Supply Study Drug | | X | | | X | | X | | X | | X | | X | | X | | X | | X | |
| Study Coordinator Call ⁿ | | | X | | | X | | X | | X | | X | | X | | X | | X | | X |
| Activities/Compliance Questionnaire ^o | | | | | | | | | | | | | X | | | | | | | |
| eCRF Completion | X | X | X | X | X | X | X | X | X | X | X | X | X | X | X | X | X | X | X | X |

Abbreviations: AE, adverse event; BCVA, best-corrected visual acuity; BL, baseline; Con Meds/Procedures, concomitant medications and concurrent procedures; eCRF, electronic case report form; EOS, end of study; ET, early termination; ETDRS, Early Treatment of Diabetic Retinopathy Study; IOP, intraocular pressure; Med Hx, medical history; Mo, month; QOL, Quality of Life; SCR, Screening.

Note: Eye assessments will be performed in both eyes at all timepoints.

^a. Screening and Day 1 procedures may be performed on the same calendar day. Ophthalmic exams performed during the screening period (within 21 days of Baseline/Day 1) do not need to be repeated on Day 1.

- b. Informed consent is an ongoing process. Participant capacity to assent will be evaluated annually; confirmation of continued affirmative assent will be sought and documented as appropriate.
- c. Demographic data will include age, sex, ethnicity/race, and eye color. Participant medical history will include parental myopia history.
- d. AEs, concomitant medications, and concurrent procedures will be monitored throughout the study, with scheduled inquiries at visits. If any issues are reported by a participant or parent/guardian, an unscheduled visit will be performed promptly to assess for AEs.
- e. Vital sign measurements will include blood pressure, heart rate, height, and body weight.
- f. Females of childbearing potential only; additional pregnancy tests may be performed at any time/day during the study. Females will be queried annually regarding childbearing potential status.
- g. The investigator's designee will administer a tolerability questionnaire to participant (or parents/guardians) to assess potential side effects of study drug (blurred vision, burning/stinging, eye pain, grittiness in eye, sensitivity to light, headache).
- h. The investigator's designee will administer a QOL questionnaire to participant (or parents/guardians)

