Descriptive statistics of the quantitative vital sign, BCVA, and IOP results will be presented by treatment group and study visit, as well as for the change from baseline at each visit. The baseline value is defined as the last non-missing value prior to the first dose of study drug. Categorical variables for biomicroscopy collection, ophthalmoscopy abnormalities, and responses to the tolerability questionnaire will be summarized by treatment group with counts and percentages of

participants in each category. Percentages will be based on the number of participants with relevant non-missing data at the visit of interest.

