All study-related raw data that support the corresponding tables and figures will be presented in data listings. Additional data listings may be generated as needed. All table, listing and figure shells will appear in landscape format employing Courier New 9-point font. Unless otherwise noted, all tables will summarize participant results by treatment group sorted in the following order: Vehicle, SYD-101 0.01% and SYD-101 0.03%. After receipt of escape therapy or re-randomization, participants will be summarized under current treatment with the treatment group divided to show initial and current treatment (e.g., Vehicle to Escape, SYD-101 0.01% re-randomized to Vehicle, etc.). Unless otherwise noted, all data listings will be sorted by treatment group and participant identification number defined as investigator identification number concatenated with the participant number. Due to family relocation or site closure, participants could be transferred from one site to a different site. In such cases, participant identification number will remain unchanged. Participants who changed study sites will be included in a data listing.

The baseline value for an assessment is defined as the last non-missing measurement including unscheduled assessments before or on the day of treatment with study drug (Day 1). Change from baseline is defined as the post-baseline value minus the baseline value for the given

assessment. Please also see Section 9 for details regarding baseline considerations for safety analyses when participants receive more than one treatment.

When study day is used for display or in comparisons, the following algorithm will be used:

- study day = date of assessment - date of first dose +1,
if date of assessment \geq first dose date.
- study day = date of assessment - date of first dose,
if date of assessment $<$ first dose date.

Note that the date of first dose is Day 1 and the day before the date of first dose is Day -1 (for analysis, there is no Day 0 for study day). First dose refers to first dose of any study treatment unless otherwise specified.

For all efficacy and safety analyses, analysis visit windows will be used for assigning assessments to an analysis visit, as per [Table 4-1](#) below.

Table 4-1 Visit Windows

Scheduled Visit	Target Day	Analysis Visit Window (Days)
Screening	-21 to 1	Not applicable
Day 1	1	Not applicable
Week 2	14	2 to 52
Month 3	91	53 to 136
Month 6	182	137 to 231
Month 9	280	232 to 322
Month 12	364	323 to 409

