7.3. Study Treatments

The active study treatment, SYD-101, is a sterile topical ophthalmic solution of atropine sulfate. The Vehicle (control) treatment formulation is identical to SYD-101, except that it does not contain active drug (atropine sulfate) and H₂O is used instead of D₂O. SYD-101 and Vehicle are clear ophthalmic solutions packaged in identical white, 5-mL low-density polyethylene (LDPE) ophthalmic bottles. Each night at bedtime, 1 drop of assigned study drug is to be instilled in each eye.

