7.3.1. Extent of Exposure

Overall duration of exposure to any study treatment is defined as the total number of days a participant is exposed to any study drug (active SYP-101 or Vehicle) during the 48 month treatment period and will be presented as the total number of days from the first dose (Day 1) to the last dose date as recorded on the EOS/ET page: (last dose date - date of first dose + 1). If the last dose date on the EOS/ET page is missing, or if a participant is lost to follow-up, the latest available visit date will be used.

Overall duration of exposure to any study treatment will be calculated at Month 24 and Month 36 as follows: (date of Month 24 [or Month 36] visit - date of Day 1 visit +1).

Additionally, participants may change study treatment due to receipt of escape medication or re-randomization at Month 36. See Table 7-1 below for potential patterns of changes to study drug doses over time (not including early discontinuations of study therapy.) Duration of exposure for

each specific treatment for each participant will be calculated as Date of Last Dose for given treatment arm – Date of First Dose for given treatment arm + 1. The start date of escape medication will be the date of the first visit where the participant's end of visit status is marked as "Continuing on Rescue Medication". The date of re-randomization at Month 36 will be used as the last dose date for SYD-101 treatment for SYD-101 0.01% and SYD-101 0.03% arm participants who are re-randomized to vehicle as well as the first dose for vehicle treatment for these participants. For the SYD-101 0.03% treatment arm, participants who are re-randomized to vehicle at Month 36 can receive SYD-101 0.03% in two non-consecutive time courses (from Baseline to Month 36 and from escape after re-randomization to Vehicle at Month 36 to Month 48), the duration of exposure for the two treatment courses will be summed to calculate the total exposure to SYD-101 0.03%.

Table 7-1 Potential Patterns of Dose Changes

Randomized Treatment	Treatment Period		Randomized Withdrawal	
	Baseline to Month 24	Month 24 to Month 36	Month 36 to 42	Month 42 to 48
SYD-101 0.01%	SYD-101 0.01%	SYD-101 0.01%	SYD-101 0.01%	SYD-101 0.01%
	SYD-101 0.01%	SYD-101 0.01%	SYD-101 0.01%	SYD-101 0.03% escape
	SYD-101 0.01%	SYD-101 0.01%	Vehicle	Vehicle
	SYD-101 0.01%	SYD-101 0.01%	Vehicle	SYD-101 0.03% escape
	SYD-101 0.01%	SYD-101 0.03% escape	SYD-101 0.03% escape	SYD-101 0.03% escape

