9.1. Adverse Events

Treatment-emergent AEs are defined as those AEs or SAEs that occur after the start of study drug dosing. All TEAEs will be summarized by treatment group (SYD 101 0.01%, SYD 101 0.03%, or Vehicle) according to treatment taken at the time of event. Adverse events with onset set more than 30 days from date study treatment discontinuation will be summarized separately. In addition, all SAEs, including deaths, will be listed and summarized separately.

For the purpose of inclusion in TEAE tables, incomplete AE start and end dates will be imputed as follows:

Missing onset dates (where UK and UKN indicate unknown or missing day and month respectively):

- UK-MMM-YYYY: If the month and year are different from the month and year of the date of first dose, assume 01-MMM-YYYY. If the month and year are the same as the month and year for the date of first dose, and the end date (after any imputation) is on or after the date of first dose, then assume the date of first dose (Day 1). If the month and year are the same as the date of first dose, and the end date (after any imputation) is prior to the date of first dose, then assume the end date for the start date.
- DD-UKN-YYYY/UK-UKN-YYYY: If the year is different from the year of the date of first dose, assume 01-JAN-YYYY of the collected year. If the year is the same as the date of first dose year, and the end date (after any imputation) is on or after the date of first dose, then assume the date of first dose (Day 1). If the year is the same as the date of first dose, and the end date (after any imputation) is prior to the date of first dose, then assume the end date for the start date.

Missing end dates (where UK and UKN indicate unknown or missing day and month respectively):

- UK-MMM-YYYY: Assume the last day of the month;
- DD-UKN-YYYY/UK-UKN-YYYY: Assume 31-DEC-YYYY

All adverse events will be classified by System Organ Class and Preferred Term (PT) according to the Medical Dictionary for Regulatory Activities (MedDRA, Version 21.0 or higher).

An overview summary of the number and percentage of participants with any TEAE, serious TEAE, treatment-related TEAE, treatment-related serious TEAE, TEAE leading to drug withdrawal, TEAE leading to study discontinuation, and AE leading to death will be provided by treatment group. The overall summaries will be presented for all adverse events, all ocular events, and all non-ocular events.

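### A Day 1 pre-dose eye finding is both baseline and treatment-emergent, and partial adverse-event onset dates in a switch month or year almost always fall before the switch

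*SAP*

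**What the plan says.** **Eye findings.** SAP 9.3.3 (ophthalmoscopy) and SAP 9.3.7 (biomicroscopy) count participants with a treatment-emergent clinically significant abnormality and use the same test: "An abnormality will be deemed treatment emergent if the onset date is on or after the date of first treatment". Neither section asks for worsening from baseline. SAP section 4 defines baseline as the "last non-missing measurement including unscheduled assessments before or on the day of treatment with study drug (Day 1"), whereas Protocol 9.4.4 is stricter: "The baseline value is defined as the last non-missing value prior to the first dose of study drug". SAP 7.3 sets the time of dosing: "Each night at bedtime, 1 drop of assigned study drug is to be instilled in each eye". Both schedules of activities place ophthalmoscopy and biomicroscopy at Screening and at Baseline, and the Protocol 1.3 footnote adds: "Screening and Day 1 procedures may be performed on the same calendar day".

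**Adverse events.** SAP 9.1 assigns treatment-emergent events to the treatment in use at the time. Its rule for an onset with unknown day reads: "If the month and year are different from the month and year of the date of first dose, assume 01-MMM-YYYY". With unknown month, onset becomes 1 January unless the year is that of the first dose. SAP section 4 explains that first dose means the first dose of any study treatment unless stated otherwise. The partial-date rules name neither re-randomization nor the start of escape medication.

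**Switch date.** In SAP 7.3.1, for SYD-101 children re-randomized to Vehicle, "The date of re-randomization at Month 36 will be used as the last dose date for SYD-101 treatment", and the same date is the first dose date of Vehicle.

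**The concern.** A treatment-emergent table should hold findings that arose or worsened after exposure. Protocol 8.3.1 defines treatment-emergent adverse events that way, and SAP 9.1 refers to events after dosing starts. A date test that includes Day 1 admits findings made hours before the first drop.

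The partial-date rules matter because the Month 36 and Month 48 safety tables are split by current treatment, and most children are due to change product at Month 36. An onset imputed to the first of the month, or to 1 January, is credited to whatever the child was using then. Events can be counted under the wrong treatment and can also drop out of the separate summary of events with onset after Month 36 (SAP 9.1.1).

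**Working it through.** No stated figure in the plan depends on these rules, so there is none to reproduce. The check applies the rules as written.

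**A. Day 1 exam.** Assume that an abnormality's onset is dated by the exam that first records it; the SAP does not define onset for exam findings.

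| Finding first recorded | Emergent under SAP 9.3.3 / 9.3.7? | Baseline-eligible under SAP 4? |
|---|---|---|
| Day before first dose | No | Yes |
| Day 1, at the visit, before the bedtime dose | Yes | Yes |
| Day after first dose | Yes | No |

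The middle row is the contradiction. It arises only if the finding is first recorded on Day 1. Exams done earlier in the 21-day screening period need not be repeated.

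**B. Partial onset dates: one example.** Take a first dose on 10 September 2019. The Month 36 target (study day 1092, SAP Table 4-1) is 5 September 2022. An event dated only September 2022 is not in the month and year of first dose, so its onset becomes 1 September 2022 (study day 1088). It goes to the treatment before the switch, whenever in September it began.

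**C. Partial onset dates: average.** Let the switch month have *m* days and the switch fall on day *d*, each day equally likely. Assume true onset is uniform over the month.

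- Imputed onset precedes the switch whenever *d* ≥ 2, a share of (*m* − 1)/*m*: 29/30 = 96.7% or 30/31 = 96.8%.
- For a given *d*, the share truly starting after the switch day is (*m* − *d*)/*m*. With *d* = 2 and *m* = 30 it is 28/30 = 93%. With *d* = 28 it is 2/30 = 7% (*m* = 30) or 3/31 = 10% (*m* = 31).
- Averaged over *d*, this is (*m* − 1)/(2*m*): 29/60 = 48.3% or 30/62 = 48.4%.
- A switch on the 1st ties with the imputed date. Leaving those cases out of the error for *m* = 30 gives (28 × 29/2)/900 = 406/900 = 45.1%. The present rule therefore misplaces 45% to 48%.
- With the month unknown in a switch year, the average share starting after the switch is 364/730 = 49.9%.

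**D. The opposite convention.** Setting such dates to the switch date, and so to the later treatment, misplaces onsets on or before day *d*. The average is 1 − 29/60 = 31/60 = 51.7%. It is no more accurate than the present rule.

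**E. Who switches.** With 280 per arm, before dropout and escape, 280 children go from Vehicle to SYD-101 0.03% and 140 + 140 = 280 go from SYD-101 to Vehicle. The present rule puts ambiguous events under Vehicle in the one group and under SYD-101 in the other.

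**The case against.** **The SAP does handle treatment boundaries.** This is right for fully dated events. Section 9 resets baseline for each treatment, and sections 9.1, 9.3.3 and 9.3.7 assign by the treatment in use. A reader might infer that the rules ignore switches altogether; they do not. The gaps are the Day 1 tie, partial dates and the unstated same-day convention.

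**Month 36 and escape exams.** It is tempting to say that findings at a switch visit are booked to the new treatment for two thirds of the children (560 of 840). The documents do not support this. The natural reading of the date of first treatment, given section 4, is the first dose of any study drug. Current treatment at a daytime exam before the bedtime dose is the old one. The 560 counts planned switchers and measures no error. Because SAP 7.3.1 gives one date to both treatments, a purely date-based program could still go wrong, so a same-day sentence is worth adding.

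**Few Day 1 findings.** Only clinically significant abnormalities count, and the protocol excludes ocular inflammation or infection and several ocular conditions. The same rule applies in all three arms. All of this stands and limits the size; the contradiction remains.

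**Imputation is only for inclusion in the emergent-event tables.** That is its stated purpose, but those tables are split by treatment at the time of the event. The event form also collects drug treatment (Protocol 8.3.5), and sites are queried about missing data (Protocol 11.1.7). These may reduce the problem, but the SAP does not name that field as the basis for attribution.

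**Bias toward the drug.** A reader might infer that the partial-date rule flatters SYD-101. It does so for Vehicle-to-0.03% children and does the reverse for SYD-101-to-Vehicle children. The net direction cannot be known from the plan.

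**Conclusion.** Both defects hold, within limits.

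- **Eye findings:** a stated rule gives a wrong result for clinically significant findings first recorded at the Day 1 pre-dose exam, provided onset is dated by that exam. The effect is a somewhat inflated emergent count for the randomized treatment, probably by few findings, with no transfer between treatments.
- **Partial dates:** in a switch month the imputed onset precedes the switch for about 97% of possible switch days, while about half of such events began after it. The half rests on uniform onset; a cluster of events soon after a switch would raise it.

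The number of partial-date events is not given, so the count of misplaced events cannot be computed. The switch problem falls mainly on the Month 48 tables. Month 36 is touched through escape and the 28 days kept after that visit. Month 24 is barely affected, because the earliest per-protocol escape is at Month 24. No efficacy result changes.

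**What to change.** **SAP 9.3.3 and 9.3.7.** Define treatment-emergent as a clinically significant abnormality at an exam after the first dose, excluding the Day 1 pre-dose exam, that is new or worse than that treatment's baseline (as set in SAP section 9) in the same eye. State that findings at a re-randomization or escape visit belong to the treatment before the switch.

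**SAP 9.1.** Flag every event whose partial onset date is compatible with either side of a switch; an event that ended before the switch is not ambiguous. Present the by-treatment adverse-event tables with flagged events assigned to the earlier treatment and again to the later one. Note that either convention alone misplaces about half under uniform onset. Replacing the present convention with the switch date would not improve accuracy.

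**Cost.** A few lines of SAP text and derivation code, and one supplementary adverse-event table. No new data are needed.
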